8.3.3.2 RELATIONSHIP TO STUDY INTERVENTION

All adverse events (AEs) must have their relationship to study intervention assessed by the principal investigator and co-investigator(s) who examines and evaluates the participant based on temporal relationship and their clinical judgment. The degree of certainty about causality will be graded using the categories below. In a clinical trial, the study product must always be suspect.

- **Definitely Related** – There is clear evidence to suggest a causal relationship, and other possible contributing factors can be ruled out. The clinical event, including an abnormal laboratory test

result, occurs in a plausible time relationship to study intervention administration and cannot be explained by concurrent disease or other drugs or chemicals. The response to withdrawal of the study intervention (dechallenge) should be clinically plausible. The event must be pharmacologically or phenomenologically definitive, with use of a satisfactory rechallenge procedure if necessary.

- **Probably Related** – There is evidence to suggest a causal relationship, and the influence of other factors is unlikely. The clinical event, including an abnormal laboratory test result, occurs within a reasonable time after administration of the study intervention, is unlikely to be attributed to concurrent disease or other drugs or chemicals, and follows a clinically reasonable response on withdrawal (dechallenge). Rechallenge information is not required to fulfill this definition.
- **Potentially Related** – There is some evidence to suggest a causal relationship (e.g., the event occurred within a reasonable time after administration of the trial medication). However, other factors may have contributed to the event (e.g., the participant's clinical condition, other concomitant events). Although an AE may rate only as "possibly related" soon after discovery, it can be flagged as requiring more information and later be upgraded to "probably related" or "definitely related", as appropriate.
- **Unlikely to be related** – A clinical event, including an abnormal laboratory test result, whose temporal relationship to study intervention administration makes a causal relationship improbable (e.g., the event did not occur within a reasonable time after administration of the study intervention) and in which other drugs or chemicals or underlying disease provides plausible explanations (e.g., the participant's clinical condition, other concomitant treatments).
- **Not Related** – The AE is completely independent of study intervention administration, and/or evidence exists that the event is definitely related to another etiology. There must be an alternative, definitive etiology documented by the clinician.

8.3.3.3 EXPECTEDNESS

The principal investigator ([name]), with input from the medical monitor ([name]) when necessary, will determine whether an adverse event (AE) is expected or unexpected in this population. The principal investigator ([name]) is an expert in non-invasive brain stimulation and the medical monitor ([name]) is an epileptologist in the department of neurology at UNC. An AE will be considered unexpected if the nature, severity, or frequency of the event is not consistent with the risk information previously described for the study intervention.

8.3.4 TIME PERIOD AND FREQUENCY FOR EVENT ASSESSMENT AND FOLLOW-UP

The occurrence of an adverse event (AE) or serious adverse event (SAE) may come to the attention of study personnel during study visits, or the study participant may report AE or SAEs outside of a scheduled study visit.

All AEs including local and systemic reactions not meeting the criteria for SAEs will be captured on the appropriate case report form (CRF). Information to be collected includes event description, time of onset, clinician's assessment of severity, relationship to study product (assessed only by those with the training and authority to make a diagnosis), and time of resolution/stabilization of the event. All AEs occurring while on study must be documented appropriately regardless of relationship. All AEs will be followed to

adequate resolution. Any medical condition that is present at the time that the participant is screened will be considered as baseline and not reported as an AE. However, if the study participant's condition deteriorates at any time during the study, it will be recorded as an AE. Changes in the severity of an AE will be documented to allow an assessment of the duration of the event at each level of severity to be performed. AEs characterized as intermittent require documentation of onset and duration of each episode.

Research personnel will record all reportable events with start dates occurring any time after informed consent is obtained until the last day of study participation. At each study visit, research personnel will inquire about the occurrence of AE/SAEs since the last visit. Events will be followed for outcome information until resolution or stabilization. All AEs including local and systemic reactions not meeting the criteria for SAEs will be captured on the appropriate case report form (CRF). Information to be collected includes event description, time of onset, clinician's assessment of severity, relationship to study product (assessed only by those with the training and authority to make a diagnosis), and time of resolution/stabilization of the event. All AEs occurring while on study must be documented appropriately regardless of relationship. All AEs will be followed to adequate resolution.

Changes in the severity of an AE will be documented to allow an assessment of the duration of the event at each level of severity to be performed. AEs characterized as intermittent require documentation of onset and duration of each episode.

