Participant Duration:	Participation for each participant will be 4 weeks. Completion includes four sessions: an EEG session, an MRI session, and two EEG-TMS sessions. The EEG session will take approximately 1.5 hours. The MRI session will take approximated 1.5 hours. The two stimulation sessions will each take approximately 2 hours. We estimate that total participation to be approximately 7 hours.

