1.3 SCHEDULE OF ACTIVITIES (SOA)

Procedures	Phone Screening	Session 1 EEG Only	Session 2 - MRI	Session 3 – EEG and TMS	Session 4 – EEG and TMS
Verbal informed consent	X				
Written informed consent		X			
Determine Eligibility	X	X			
MRI Screening	X		X		
TMS Screening	X	X		X	X
Demographics	X				
SHAPS		X			
RRS		X			
BIS/BAS		X			
TEPS		X			
STAI		X			
Urine Pregnancy Test (if applicable)		X			
Resting-state with EEG		X		X	X
S-EEfRT with EEG		X		X	X
EMG recorded		X		X	X
Structural MRI			X		
S-EEfRT with functional MRI			X		
Motor threshold using single pulse TMS		X			
TMS tolerability test		X			
S-EEfRT with patterned TMS				X	X
Stimulation Questionnaire		X		X	X
AE Structured Interview		*		*	*
AE Review and Evaluation		*		*	*

* when applicable

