Risk of Injury and Discomfort: Transcranial magnetic stimulation has been cleared for use in the USA by the FDA. TMS (the methodology used in this experiment) has nothing to do with electroconvulsive therapy that applies many orders of magnitude higher stimulation current. The level of electrical stimulation produced by TMS is within the range of activity that is endogenous to the brain. Furthermore, the intensity of stimulation is calibrated to the sensitivity of the individual participant such that the level of stimulation is matched to that of naturally occurring activity. In order to monitor side-effects, we will be administering an adverse effects stimulation questionnaire after each stimulation session to determine whether these effects were experienced. Research personnel present during these sessions will also check with the participant periodically during the stimulation to see whether they are comfortable. If any side-effect occurs that is rated by the participant and confirmed by the researcher to be stronger than "moderate," the stimulation will be immediately stopped.

Risk of Psychological Discomfort: There is a psychological element in that some participants may become claustrophobic upon entering the small space of the MRI bore. To reduce psychological distress, participants are informed that they can withdraw consent and stop participation at any time. Participants are monitored throughout the MRI scans and can terminate the scan at any time by squeezing a ball held in the hand, and will be quickly removed from the MRI bore. There is additionally a risk of psychological discomfort from receiving transcranial magnetic stimulation (TMS). Due to the discomfort from receiving TMS and the proximity of the TMS coil to the face and head of the participant, this can result in psychological discomfort. Similar to MRI, participants are informed that they can withdraw consent and stop participation at any time. Participants are monitored throughout the TMS sessions and can stop receiving stimulation at any time by physically moving away from the TMS coil. The field of stimulation is less than a couple centimeters. Furthermore, researchers monitor the participant throughout stimulation and will check in with the participant approximately every 5 minutes between each task block.

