Risk of Injury from MRI: MRI will be conducted within the Biomedical Research Imaging Center (BRIC) at UNC Chapel Hill. The BRIC has a full-time staff that is well trained in the safety involved with MRI. Participants complete a contraindications form for MRI upon enrollment in each study. Any questions or concerns from the researcher can be addressed by the staff at the BRIC. In addition, the participant completes an additional screening form in the presence of the staff at the BRIC to further ensure that all safety concerns are addressed. The specific risks that are presented to the participant are avoided by effective screening. These risks include physical injury from the presence of metal within the body or in the environment when entering the magnetic field of the MRI. The strong magnetic field will pull metal towards the center of the field. Thus, it is imperative that all metal is removed from the body and any participants with metal within the body do not enter the field. The MR technicians at the BRIC maintain strict boundaries and screening via metal detector before entering rooms near to the MRI, adjacent to the MRI room, and the MRI room. This three-staged system is standard practice for MRI. Participants are provided with a medical gown and private changing room within the BRIC. This ensures that there is no chance that participants will enter the room with metallic objects in their pockets (e.g., phones or wallet). In addition, technicians screen participants and walk through a check list. Another risk from the MRI is the chance of a skin burn from clothing that contains metallic microfibers/particles. Thus, participants wear a medical gown to avoid the complication from modern athletic clothing technology. These risks are well-understood by the scientific community and extensive safety procedures are put in place by regulatory oversight that are maintained by the BRIC.

Risk of Transient Psychological Changes from TMS: There is a rare risk that TMS will result in alterations in mood, trouble concentrating, or sleepiness. These side effects are not commonly reported, but given the diversity of cognitive functions that the prefrontal cortex supports, TMS could potentially produce a transient change in the above listed cognitive functions.

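### Adverse events that start after a participant's last TMS exposure are neither asked about nor inside the recording window, and the schedule has no row for the inquiry that 8.3.4 promises

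*Combined protocol and SAP*

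**What the plan says.** Section 8.3.4 sets the ascertainment rule: "At each study visit, research personnel will inquire about the occurrence of AE/SAEs since the last visit". It sets the recording window as start dates "any time after informed consent is obtained until the last day of study participation". It also accepts reports volunteered between visits, and it follows events already recorded until they settle.

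The synopsis (1.1) fixes the number of visits: "Completion includes four sessions: an EEG session, an MRI session, and two EEG-TMS sessions". Section 4.4 ends the study at the final session of the 24th completer. Neither section, nor the schedule in 1.3, describes a visit or contact after session 4.

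TMS is given on three occasions: abbreviated tolerability blocks at the end of session 1, and full stimulation in sessions 3 and 4 (4.3). Section 2.3.4 has a side-effect questionnaire follow every TMS session, and 1.3 marks it at sessions 1, 3 and 4.

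The schedule has two adverse-event rows, "AE Structured Interview" and "AE Review and Evaluation". Both are marked at sessions 1, 3 and 4, only where applicable, and both are blank at session 2. There is no row for the visit-by-visit inquiry.

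**The concern.** An inquiry that looks back from the next visit works only if there is a next visit. After session 4 there is none. The questionnaire that day is completed once stimulation ends, so it cannot detect anything that begins later. An event that starts in the evening of session 4 is inside the window by date but reaches the record only if the participant volunteers it. An event that starts the next day is outside the window even if it is volunteered.

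Section 2.3.1 names seizure, mood change, trouble concentrating and sleepiness as risks of TMS. Section 8.3.4 plainly expects some events to begin between visits, since it asks about that interval. Section 9.4.1 says that effects last a second or two, but that concerns the expected effect of stimulation on the task and is not a reason to stop asking about adverse events. Section 7.2 also suggests that the tolerability information may be useful to other researchers and clinicians, so incomplete ascertainment after the last exposure would carry over into that use.

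The schedule is a smaller matter. Staff who work from 1.3 see no prompt to ask about adverse events at session 2, although 8.3.4 requires it and session 2 is the first visit after the first TMS exposure.

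**Working it through.** The plan states no figure to reproduce here. The check is a count of exposures against inquiries, plus one dose calculation.

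**Inputs.** Visits 1, 2, 3 and 4 (1.1, 1.3). TMS exposures at sessions 1, 3 and 4, MRI at session 2 (1.3, 4.3). Six blocks of 30 trials per TMS session and 15 pulses per trial (4.3). Target of 24 completers, enrolment ceiling of 50 (9.2). Up to 30% excluded after session 1 (5.4).

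**Size of the last exposure.** 6 x 30 = 180 trains per session. 180 x 15 = 2,700 pulses. Two main sessions: 2 x 2,700 = 5,400. Session 4 share: 2,700 / 5,400 = 50%. This measures exposure; it does not estimate missed events.

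**Which aftermaths are asked about, under three readings.**

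- *Text of 8.3.4 as written.* Session 1 aftermath: asked at session 2. MRI aftermath: asked at session 3. Session 3 aftermath: asked at session 4. Session 4 aftermath: never asked. Uncovered: 1 of 3 TMS exposures.
- *Schedule marks taken as the only inquiry points, looking back to the last inquiry.* Session 3 covers everything since session 1, including the MRI, and session 4 covers session 3. Uncovered: 1 of 3, again session 4.
- *Schedule marks taken as the only inquiry points, looking back strictly to the previous visit.* The interval from session 1 to session 2 is missed, session 3 still covers the time since the MRI, and session 4 covers session 3. Uncovered: 2 of 3 (sessions 1 and 4).

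The session 4 gap appears under all three readings. The session 1 gap appears only under the third. The MRI aftermath is covered under all three.

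**Participants who do not complete.** The caption in 1.2 puts the tolerability TMS before exclusion on task performance, and 5.4 expects up to 30% to be excluded after session 1. Read in that order, and assuming enrolment reaches its ceiling, up to 0.30 x 50 = 15 people would receive TMS and have no next visit. Section 7.1 ends participation with no further sessions when stimulation is discontinued in session 3 or 4, so those people also have no later scheduled inquiry. The look-back fails for whichever TMS exposure is a person's last.

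**After the fix.** With a contact after the last exposure and a matching window, the uncovered count under 8.3.4 falls from 1 of 3 to 0 of 3. With session 2 also shown in the schedule, the worst reading falls from 2 of 3 to 0 of 3.

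**The case against.** The strongest reply is that the plan has several layers of safety capture and that the schedule's blanks mean little. Much of this stands.

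- The questionnaire covers same-day effects of every TMS exposure, volunteered reports are accepted, recorded events are followed up, and TMS contraindications are screened again at sessions 3 and 4.
- The blank session 2 cells belong to the structured interview, which a very high questionnaire rating triggers (2.3.4, 4.1), and to the review step. No TMS and no questionnaire at session 2 means no interview, so the blanks fit that trigger. Nor is the schedule a complete list of verbal questions: 8.3.6 has a pregnancy question at each session that 1.3 does not show.
- The documents give no rate of delayed events, so no number of missed events can be derived.
- Consent pages are not in the reviewed text, so any instruction there about contacting staff after a session cannot be judged.

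A reader might infer three stronger things that the documents do not support.

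1. *That two of three TMS exposures go unasked.* This needs the schedule to override the explicit rule in 8.3.4, and a strict look-back at session 3 over a visit at which nobody asked.
2. *That MRI events go unasked.* Section 2.3.1 names them: "Another risk from the MRI is the chance of a skin burn from clothing that contains metallic microfibers/particles" and "some participants may become claustrophobic upon entering the small space of the MRI bore". But participants are monitored throughout the scan, and the session 3 inquiry covers the time since it.
3. *That the dlPFC versus mPFC comparison in 9.4.5 is biased.* Among completers, delayed events from a main session are solicited only for the site stimulated in session 3, so for 24 / 2 = 12 participants per site. But that comparison rests mainly on the questionnaire after sessions 3 and 4, which covers both sites in every completer. Site order is counterbalanced, so no direction of bias is shown. The session 1 blocks also stimulate both sites, and 8.3.4 has their aftermath asked about at session 2.

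None of this supplies an inquiry after session 4, or a window that would accept what such an inquiry found.

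**Conclusion.** The gap is real and narrow. Followed exactly, the plan neither solicits nor records events that start after the day of a participant's last TMS exposure. For completers this is 1 of 3 exposures, the one being a full session with half of the main-session pulses. It also reaches people who leave after session 1 TMS, up to 15 under the assumptions shown, and those halted in session 3 or 4.

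This rests on reading the last day of participation as the day of the final session attended. That is an inference, but no later contact is described. How many events would be missed is unknown.

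The mismatch between 8.3.4 and 1.3 over session 2 is a separate matter of documentation. It becomes a second gap in ascertainment only if staff treat the schedule as controlling. The change is worth making because it is cheap and concerns safety; the primary and secondary efficacy analyses are not affected.

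**What to change.** 1. In 8.3.4, add one brief phone or email inquiry about adverse events after each participant's last TMS exposure. Include those who leave after session 1 and those halted in session 3 or 4. Extend the recording window to that contact. The sponsor should set and state the interval; the documents give no spacing between sessions from which to derive one.
2. In 1.3, add a separate adverse-event inquiry row marked at sessions 2, 3 and 4, plus the new contact, so that the schedule matches 8.3.4. Leave the structured interview conditional, as its trigger in 2.3.4 and 4.1 intends.

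The cost is a wording change in two sections and a few minutes per participant for staff who already make reminder calls or emails (5.5). Some participants will not reply, so the number reached should be reported next to any count of delayed events.

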8.3.5 ADVERSE EVENT REPORTING

We will be adopting the following reporting procedures:

What event is reported	When is event reported	By whom is event reported	To whom is event reported
Fatal or life-threatening unexpected, suspected serious adverse reactions	Within 24 hours of initial receipt of information	Investigator	
• Local/internal IRB
Non-fatal, non-life-threatening unexpected, suspected serious adverse reactions	Within 48 hours of initial receipt of information	Research Personnel	
• Local/internal IRB
Unanticipated adverse device effects	Within 10 working days of investigator first learning of effect	Investigator	
• Local/internal IRB
Unanticipated Problem that is not an SAE	Within 7 days of the investigator becoming aware of the problem	Investigator	
• Local/internal IRB

8.3.6 REPORTING OF PREGNANCY

There have been scientific studies using transcranial magnetic stimulation in pregnancy (see (Damar et al. 2020; Konstantinou et al. 2020) for review). None of these studies reported side-effects specific to pregnancy or fetal development. Nonetheless, pregnant women will be excluded from this study because they are a protected group. Female participants will be asked if there is a possibility that they are pregnant at each session. If the participant says yes or is unsure, then we will verify pregnancy status via a urine pregnancy test. Only upon a verbal confirmation that pregnancy is not possible or a negative finding from a pregnancy test will we proceed with the experiment.

8.4 UNANTICIPATED PROBLEMS

8.4.1 DEFINITION OF UNANTICIPATED PROBLEMS (UP)

The Office for Human Research Protections (OHRP) considers unanticipated problems involving risks to participants or others to include, in general, any incident, experience, or outcome that meets all of the following criteria:

- Unexpected in terms of nature, severity, or frequency given (a) the research procedures that are described in the protocol-related documents, such as the Institutional Review Board (IRB)-approved research protocol and informed consent document; and (b) the characteristics of the participant population being studied;
- Related or possibly related to participation in the research (“possibly related” means there is a reasonable possibility that the incident, experience, or outcome may have been caused by the procedures involved in the research); and
- Suggests that the research places participants or others at a greater risk of harm (including physical, psychological, economic, or social harm) than was previously known or recognized.

8.4.2 UNANTICIPATED PROBLEM REPORTING

If a UE occurs, the IRB will be notified, and the study will be adjusted as needed to protect the health and safety of the participants. Depending on the nature of the UE, the research protocol, inclusion/exclusion criteria, and informed consent will be changed to reflect the possibility of this event reoccurring. During this time, no new participants will be recruited and the research procedures for currently enrolled participants will be stopped. Each UE will be recorded and reported throughout the study.

